The Evaluation of Thrombogenecity in Patients Undergoing WATCHMAN Left Atrial Appendage Closure (TARGET-WATCHMAN) Trial

Principal Investigators: [name].

Device Name: The WATCHMANTM Device

Sponsor: Boston Scientific, Inc.

Site of Investigation: Inova Heart and Vascular Institute at Inova Fairfax Hospital, Falls Church, VA

Date of Protocol: 5 January 2018

Contact Information:

[name]. Inova Center for Thrombosis Research and Drug Development Inova Heart and Vascular Institute [name] [contact] [contact] Email: [contact]

PROTOCOL SYNOPSIS

Title: The evaluation of thrombogenecity in patients undergoing WATCHMAN left atrial appendage closure trial

Short Title: TARGET-WATCHMAN

Rationale: The results of this study will aid clinicians in better risk stratification of patients undergoing WATCHMAN left atrial appendage closure to prevent future thromboembolic and bleeding events. Additionally, the information will help guide the management of anticoagulation post-WATCHMAN implant, in particular the duration of anticoagulation and anti-platelet therapy.

Objectives

Primary: To identify biomarkers, parameters of thrombosis and platelet function to assist in identification of a thrombogenic phenotype in patients undergoing implantation of the WATCHMAN left atrial appendage closure device.

Secondary:

1. Determine differences in thrombogenicity among patients undergoing WATCHMAN left atrial appendage closure pre- and up to 1 year post- implant.

2. Identify blood biomarkers for predicting thrombo-embolic events and/or presence of LA thrombus detected on TEE performed 45 days, and at 1-year post-WATCHMAN implant.

3. Identify blood biomarkers for predicting major or clinically relevant non-major bleeding (CRNM) up to 1-year post-WATCHMAN implant.

5. Determine frequency of high on-treatment platelet reactivity and correlate to outcomes.

6. Determine frequency of low, medium, and high risk thrombogenic phenotype within the study population.

7. Identify changes in Galectin-3 and sST2 post-WATCHMAN implant and correlate to other biomarkers studied.

Study Type: Observational study design.

Study Design: Prospective, single center, observational study.

Study Methodology: This investigation will be conducted in subjects >18 years of age scheduled for WATCHMAN device implantation procedure. The study explores novel biomarkers to assess thrombogenicity in patients undergoing WATCHMAN left atrial appendage closure. Patients will undergo serial assessment of thrombogenicity and fibrosis over a twelve-month follow-up.

Patients: A total of 30 patients receiving WATCHMAN device implantation. It is expected that an additional 10 patients may be required to be enrolled to account for screen failures.

Statistical Methodology: Pearsons' correlation coefficient, univariate and multivariate logistic regression models, ROC curve analysis. Statistical calculations will be carried out using SAS® for Windows, version 9.3 or later (Cary, NC).

1 INTRODUCTION

1.1 Specific Aims

- To quantify and characterize specific biomarkers of thrombogenicity in patients undergoing WATCHMAN implant, both pre- and post-procedure.
- To identify variations in thrombogenic phenotypes which play a role in the varied incidence of thromboembolic complications amongst patients undergoing percutaneous left atrial appendage closure with the WATCHMAN implant
- Obtain pilot data for future translational trials aimed at personalizing antithrombotic therapy (duration of anticoagulation and anti-platelet therapy) by thrombogenic phenotype in WATCHMAN patients.

1.2 Hypothesis

We hypothesize that serial evaluation of (a) platelet activation and aggregation, (b) intrinsic thrombogenicity measured by thrombelastography, and (c) selected biomarkers will provide the "blueprint" of individual hemostasis to precisely characterize patients who have thrombotic or bleeding tendencies. The latter will facilitate future efforts to personalize antithrombotic therapy regimens during and following WATCHMAN implant.

1.3 Background and Significance

Atrial fibrillation (AF) is associated with an increased risk of stroke and thromboembolism.¹ Anticoagulation, with either warfarin or the novel anticoagulants (NOACs) is recommended for patients at increased risk of stroke, based on the CHA2DS2-VASc scoring system. However, treatment with these agents is not without its limitations and may be associated with serious side effects, of which major gastrointestinal bleeding and hemorrhagic stroke are the most devastating. Non-pharmacologic strategies for stroke prevention in patients with atrial fibrillation exist. Percutaneous left atrial appendage closure with the WATCHMAN device is an FDA approved modality, and exists as an option for stroke reduction in patients with atrial fibrillation, deemed to be at high risk for long term anticoagulation.

Current guidelines for WATCHMAN implant require that a patient must be treated with at least 45 days of warfarin post WATCHMAN implant and then six months of a combination of aspirin and clopidogrel. This duration of therapy is based on the data from two large clinical trials (Protect AF and Prevail) involving WATCHMAN implant and several CAP registries.²⁻⁵

No data exists on whether there are differences in markers of thrombogenicity among patients undergoing WATCHMAN implant, and whether those differences could be used to guide the management of anticoagulation and anti-platelet therapy pre- and post-WATCHMAN implant. The purpose of this study will be to quantify and characterize specific biomarkers of thrombogenicity in patients undergoing WATCHMAN implant, both pre- and post-procedure. In addition, we seek to find variations in thrombogenic phenotypes which play a role in the varied incidence of thromboembolic complications amongst patients undergoing percutaneous left atrial appendage closure with the WATCHMAN implant. Furthermore, the individual thrombogenic phenotype may be used to guide anticoagulation in these patients, more specifically the duration of anticoagulation and anti-platelet therapy. This will be established by utilizing biomarkers assessed by thrombelastography (TEG), platelet aggregation, CAT assay, fibrinogen levels, urinary thromboxane, D-dimer, CRP and PAI-1. We hypothesize that by utilizing these assays, we can accurately identify a thrombogenic phenotype in patients undergoing WATCHMAN implant for left atrial appendage closure and help predict and manage the risk of subsequent thrombotic complications. The proteins soluble ST2 (sST2) and galectin-3 are currently gaining mounting interest as candidate biomarkers in cardiac disease which have been utilized to measure acute inflammation to chronic inflammation and tissue fibrinogenisis. In this pilot study, we will assess changes in Galectin-3 and sST2 post-WATCHMAN implant and correlate to other biomarkers studied.

2 POST-IMPLANTATION CARE

The device implantation procedure is performed in a standard fashion per device implant protocol in the cardiac catheterization laboratory. Device selection is based on accurate left atrial appendage measurements obtained in multiple angles. The device is permeable to blood thus patients require post-procedure warfarin therapy for 45 days on a dose assuring a therapeutic INR level and ASA 81mg. A transesophageal echocardiography (TEE) is performed for device assessment 45 days post-procedure after which a decision is made to discontinue warfarin. If the TEE shows no leak > 5mm around the device and no left atrial (LA) thrombus, warfarin is discontinued and the patient is treated with clopidogrel 75 mg and aspirin 325mg for up to 6 months, after which the clopidogrel is discontinued and aspirin 162-325mg thereafter. If the follow-up TEE at 45 days shows a leak > 5mm around the device or a LA thrombus is noted, the patient will need to remain on warfarin for another 6 months (or upon resolution of thrombus), and another TEE performed thereafter.

If the TEE performed at 45 days shows that the opening of the LAA is not adequately closed, another TEE may be scheduled at around 6 months to re-evaluate whether adequate closer of the LAA has occurred. At about 12 months after the WATCHMAN implant, another TEE is performed to check on the device and make sure that the LAA is still closed.

3 STUDY DESIGN AND SUBJECT SELECTION

3.1 Study Type

This is an observational study that will be conducted in subjects scheduled for the WATCHMAN device implantation. The laboratory assessments (see section 1.1) will be performed at the baseline (pre-procedure), post-implantation, 45 days, 6 months, and 12 months post-procedure (see table 1).

3.2 Duration of Study

Subject participation will be for 12 months after obtaining consent.

3.3 Number of Subjects

Thirty patients scheduled for WATCHMAN device implantation.

3.4 Study Population

3.4.1 Population Characteristics

3.4.1.1 Gender and racial and ethnic origin of subjects

The study's intended population is inclusive of both genders (males and females), and all racial and ethnic groups and subgroups.

3.4.1.2 Age of subjects

Subject enrollment will be comprised of subjects >18 years of age.

3.4.2 Vulnerable Population

Children, pregnant women, institutionalized persons, and persons with decisional incapacity will be not be enrolled in this study.

3.5 Recruitment

Recruitment will occur at the Inova Heart and Vascular Institute. The expected length of the recruitment period is 16 months. The average number of WATCHMAN left atrial appendage closure procedures performed at INOVA is approximated to be 60 per year. If the study conduct (e.g. recruitment rate; drop-out rate; data quality; protocol compliance) does not suggest a proper completion of the trial within the reasonable time frame as agreed upon, the recruitment period may be extended to reach the desired sample size.

3.6 Inclusion Criteria

- o Subject indicated and scheduled for WATCHMAN device implantation at IHVI.
- o Subject may be of either sex and of any race, and must be >18 years of age.
- o Subject must be willing and able to give appropriate informed consent.
- o The subject is able to read and has signed and dated the informed consent document including authorization permitting release of personal health information approved by the investigator's Institutional Review Board (IRB).

3.7 Exclusion Criteria

Subjects will be excluded from entry if ANY of the criteria listed below are met:

- Subjects with contraindications for WATCHMAN device implantation
 - Intracardiac thrombus is visualized by echocardiographic imaging
 - An atrial septal defect repair or closure device or a patent foramen ovale repair or closure device is present
 - The LAA anatomy will not accommodate a device
 - Any of the customary contraindications for other percutaneous catheterization procedures (e.g., patient size too small to accommodate TEE probe or required catheters) or conditions (e.g., active infection, bleeding disorder) are present.
 - There are contraindications to the use of warfarin, aspirin, or clopidogrel
 - The patient has a known hypersensitivity to any portion of the device material or the individual components such that the use of the WATCHMAN Device is contraindicated
- Ligated or oversewn left atrium
- Concurrent participation in any investigational study

- Subject likely to not be available to complete all protocol-required study visits or procedures, to the best of the subject's and investigator's knowledge
- History or evidence of any other clinically significant disorder, condition, or disease other than those outlined above that, in the opinion of the investigator, may compromise the ability of the subject to give written informed consent, would pose a risk to subject safety or interfere with the study evaluation, procedures, or completion.

4 STUDY METHODS

4.1 Laboratory Measurements

Phlebotomy sites will be carefully chosen to minimize risk and platelet activation. In addition, blood from the left atrium via transeptal sheath will be collected during the procedure to compare clotting at the site of implant and the periphery. After discarding the first 2-3mL of free flowing blood, the blood collection tubes will be filled to capacity and gently inverted 3 to 5 times to ensure complete mixing of the anticoagulant. At each visit blood (total=approximately 17 ml each visit) will be collected in two 3.2% trisodium citrate tubes (light transmittance aggregometry and thrombelastography), one CTAD tube containing buffered citrate solution, theophylline, adenosine and dipyridamole (activation markers) and one serum separator tube (lipid and biomarker measurements).

 Platelet Aggregation by Light Transmittance Aggregometry (LTA) (Chronolog) Platelet aggregation will be assessed in platelet-rich plasma using a Chronolog Lumi-Aggregometer (model 490-4D) with the AggroLink software package after stimulation with 5 and 20 µM ADP, 2mM AA, and 4ug/ml collagen.⁶

• TEG6S with citrated multi-channel cartridge

The TEG6s instrument is a microfluidic fully automated cartridge-based device. The standard hemostasis assay cartridge (Citrated Multi-Channel, CMC) uses a citrated blood sample that is mixed with dried reagents within each of the 4 channels, each with calcium chloride (to reverse the sodium citrate) and: (1) kaolin, (2) kaolin+ tissue factor activated (RapidTEG), (3) kaolin + heparinase, and (4) kaolin + abciximab (functional fibrinogen).⁷

- *Thrombogram (CAT assay)*: Uses a slow fluorogenic thrombin substrate and continuous comparison to a simultaneously run calibrator, thrombin generation can be monitored automatically, on line, in clotting PPP or PRP at a throughput of up to 100 samples per hour. The resulting "Thrombogram" in PPP measure patients with hypo- or hypercoagulable phenotypes.⁸
- Urinary 11-dehydrothromboxane B2 (UTBx): Measures endogenous platelet activation.⁹
- *Soluble biomarkers* (fibrinogen, d-dimer, hsCRP, and PAI) to indicate thrombogenicity, oxidative stress, endothelial dysfunction, and inflammation.
- *Markers of fibrosis:* sST2 and Galectin-3 markers measure maladaptive response to tissue fibrosis.¹⁰

4.2 Primary and Secondary Objectives

4.2.1 Primary Objective

To identify biomarkers, parameters of thrombosis and platelet function to assist in identification of a thrombogenic phenotype in patients undergoing implantation of the WATCHMAN left atrial appendage closure device.

- 4.2.2 Secondary Objectives
 - Identify blood biomarkers for predicting thrombo-embolic events and/or presence of LA thrombus detected on TEE performed 45 days, and at 1-year post-WATCHMAN implant.
 - Determine differences in thrombogenicity among patients undergoing WATCHMAN left atrial appendage closure pre- and up to 1 year post- implant.
 - Identify blood biomarkers for predicting thrombo-embolic events and/or presence of LA thrombus detected on TEE performed 45 days, and at 1-year post-WATCHMAN implant.
 - Identify blood biomarkers for predicting major or clinically relevant non-major bleeding (CRNM) up to 1-year post-WATCHMAN implant.
 - Determine frequency of high on-treatment platelet reactivity and correlate to outcomes.
 - Determine frequency of low, medium, and high risk thrombogenic phenotype within the study population.
 - Identify changes in Galectin-3 and sST2 post-WATCHMAN implant and correlate to other biomarkers studied.
- 4.2.3 Clinical Endpoints
 - Thrombo-embolic events (Death, Stroke, and MI) and/or presence of LA thrombus detected on TEE.
 - Bleeding using Academic Research Consortium (BARC) definition.

4.3 Informed Consent

The research staff will meet with the participant to discuss the study, explain the goals, risks/benefits, answer questions, while allowing adequate time and privacy for decision making, and then obtaining a signed consent document. Patients incapable of providing consent due to a medical situation will not be approached for study participation. No study related procedures may commence without a signed consent form.

5 STATISTICAL CONSIDERATIONS/DATA ANALYSIS

5.1 Statistical Calculations

No data exists on whether there are differences in markers of thrombogenicity among patients undergoing WATCHMAN implant, and if those differences could be used to guide the management of anticoagulation and anti-platelet therapy pre- and post-WATCHMAN implant. Similar pharmacodynamic studies conducted in device trials (Coronary Stent, TAVR) have typically enrolled 30- 75 patients to determine serial changes in thrombogenicity and in biomarkers after implant. No similar size analysis has been

performed with WATCHMAN patients. As such a reasonable calculation of a sample size based on the accepted error rate is currently not feasible.

5.2 Statistical Analysis

Categorical variables will be expressed as n (%). Continuous variables with normal distributions will be reported as mean [standard deviation (SD)], while variables not having a normal distribution were reported as median (interquartile). Wilcoxon signed rank tests or paired t-tests will be performed to test differences in lab values before and after implant. Correlation analysis will be performed by Pearson's correlation coefficient. Univariate and multivariate logistic regression models will be used to determine predictors of clinical endpoints. The predictive cut-point values of platelet function tests or rate of fibrinolysis will be assessed by ROC curve analysis. Statistical calculations will be carried out using SAS® for Windows, version 9.3 or later (Cary, NC).

5.3 Future Experiments:

Our initial pilot study will allow for adjustments to our experimental methodology and will provide insights into the potential value of this analysis for determining an individual WATCHMAN recipient's degree of antithrombotic therapy. If our pilot data is interesting we then plan to expand our analysis to a consortium of WATCHMAN research centers. A larger cohort will allow validation of our initial findings. Future experiments will then focus on titration of anticoagulation and antiplatelet therapy to reduce the risk of bleeding and thrombotic complications. In addition, the individual thrombogenic phenotype may be used to guide anticoagulation in these patients, more specifically the duration of anticoagulation and anti-platelet therapy. To facilitate these and future studies, we plan to submit our pilot data generated from this grant as part of future grant applications.

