6 VISIT SCHEDULE AND ASSESSMENTS

Informed consent will be obtained from subjects meeting the inclusion criteria and none of the exclusion criteria before the initiation of any study-specific procedures. The study comprises of 4 periods: (1) Procedural (pre and post WATCHMAN implantation, (2) 45 days post-procedure, (3) 6 months post-procedure, and (4) 12 months post-procedure. Required assessments for each study visit are listed in Table 1. Subjects should be seen for visits on the designated day or according to the allowed window period (see Table 1).

Each clinic visit includes laboratory measurements, safety assessment, and health and concomitant medication review. A complete physical exam is required for visit 1 (baseline).

• Laboratory measurements

Laboratory measurements (see section 4.1) will be obtained at baseline (prior to device implantation procedure), immediately post-procedure, 45 days, 6 months, and 12 months post-procedure. Laboratory measurements needed at baseline and immediately post-procedure will be done while the subject is on the pre-op area, angiography suite, and/or recovery area. The study will require clinic visits during the required laboratory measurements for 45 days, 6 months, and 12 month post-procedure.

• Health and concomitant medication review

During the follow-up clinic visits, changes in participant's medical condition (any new diagnosis, etc.) and concomitant medications should be updated. Note that only anticoagulation and anti-platelet therapies will be collected. Adverse events will be reported, side effects and symptoms assessed.

• Physical Exam

A physical exam will be conducted by the investigator during the screening period after obtaining consent to evaluate the general status of the subject and to further elucidate patient symptoms, risk factors, or concerns that may increase the subject's risk for adverse events.

• Safety assessments

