Safety assessments will consist of monitoring and recording of serious adverse events (see section 10). The occurrence of adverse events should be sought by non-directive questioning of the subject at each visit during the study. AEs may also be detected when these are volunteered by the subject during or between visits or through physical examination, laboratory test, or other assessments. For the purpose of this study, only (a) thromboembolic and (b) bleeding events, and (c) serious adverse events (SAEs) directly related to study procedures, or (d) SAEs not previously reported to a left atrial appendage closure device or implantation (see device package insert) with potential relatedness to the WATCHMAN device will be collected and reported (see section 10).

Additional assessments required to ensure safety of subjects should be administered as deemed necessary by the investigator on a case by case basis.

	V1		V2 ⁵	V3 ⁵	V4 ⁵
	Pre- procedure	Immediately post- procedure	45 days post- procedure (+ 10 days)	6 months post- procedure (+ 1 month)	12 months post- procedure (+ 1-month)
Informed Consent	Х				
Inclusion/Exclusion Criteria	Х				
Medical History	Х				
Review Prior/Concomitant Medications ¹	Х	Х	Х	Х	Х
Physical Examination	Х				
Height, weight, Blood pressure, heart rate measurements	Х				
TEE ²	Х		X		Х
Laboratory Measurements: TEG6S and platelet aggregation	Х	Х	Х	Х	Х

Table 1Schedule of Events

	V1		V2 ⁵	V3 ⁵	V4 ⁵
	Pre- procedure	Immediately post- procedure	45 days post- procedure (+ 10 days)	6 months post- procedure (+ 1 month)	12 months post- procedure (+ 1-month)
Laboratory Measurements: Thrombogram (CAT assay), urinary thromboxane,biomarkers, markers of fibrosis	Х	X ⁶	Х	Х	X ³
Adverse events ⁴	Х	Х	Х	Х	Х

¹Anticoagulation and anti-platelet therapies only

² Standard of care procedure

³ Thrombogram, urinary thromboxane, biomarkers, and markers of fibrosis obtained only if subject have reports of thromboembolic events post-implantation

⁴Only thromboembolic and bleeding events, SAEs not previously reported to WATCHMAN device or implantation procedure (see device package insert) with potential relatedness to the WATCHMAN device/implantation procedure and SAEs directly related to study procedures will be collected ⁵The 45 days, 6 months, and 12 month visits post-procedure coincide with recommended standard of care follow-up visits post-WATCHMAN implantation procedure.

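### Section 5.2 plans logistic prediction models and ROC cut-points in at most 30 patients with no control of overfitting or marker selection and no stated predictor sampling time, so apparent discrimination will be biased upward

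*Combined protocol and SAP*

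**What the plan says.** Section 5.2 gives the prediction analysis in two sentences: "Univariate and multivariate logistic regression models will be used to determine predictors of clinical endpoints", and "The predictive cut-point values of platelet function tests or rate of fibrinolysis will be assessed by ROC curve analysis". The ROC sentence names no outcome.

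The sample is set in Section 3.3: "Thirty patients scheduled for WATCHMAN device implantation". The ten extra enrolments in the synopsis replace screen failures, and Section 6.1.2 exits failed implants, so 30 is a ceiling for the analysed set. Section 5.1 declines a sample-size calculation. It relies on device studies that "have typically enrolled 30- 75 patients to determine serial changes in thrombogenicity and in biomarkers after implant", which is a different task from predicting clinical events.

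Section 4.2.2 contains two prediction objectives. One concerns thromboembolism or left atrial thrombus; the other reads "Identify blood biomarkers for predicting major or clinically relevant non-major bleeding (CRNM) up to 1-year post-WATCHMAN implant". A third asks that high on-treatment platelet reactivity be correlated with outcomes.

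Section 6 says laboratory measurements "will be obtained at baseline (prior to device implantation procedure), immediately post-procedure, 45 days, 6 months, and 12 months post-procedure". Table 1, footnote 3, limits the 12-month thrombogram, urinary thromboxane, biomarker and fibrosis assays: they are "obtained only if subject have reports of thromboembolic events post-implantation". Sections 6 and 6.1.3 both refer the reader to Table 1 for what each visit requires.

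**The concern.** With few events and many candidate markers, some marker will separate event from event-free patients by chance. A cut-point placed on the same data inherits that optimism. Nothing in Section 5.2 limits, measures or corrects it.

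Sampling time is a second gap. Five draws are scheduled, and no passage says which one enters a regression or ROC curve. The day-45 blood draw and day-45 TEE fall at the same visit. A marker measured then describes association with a thrombus already present, not prediction of it.

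Two secondary objectives rest on this analysis, as does the outcome part of a third. Section 5.3 makes expansion to a consortium depend on how the pilot data look and plans to use them in grant applications. An analysis that often looks promising when no marker predicts anything is a weak basis for that decision.

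**Working it through.** There is no stated figure to reproduce: the plan gives no event rate, error rate, power or effect size.

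**Inputs from the documents.** N = 30 (Section 3.3). Markers for the ROC sentence: four aggregometry readings (5 and 20 µM ADP, AA, collagen; Section 4.1) plus one fibrinolysis rate, so k = 5. Urinary thromboxane, which Section 4.1 says "Measures endogenous platelet activation", could make it 6. The logistic sentence is not restricted by marker. Section 4.1 lists about 4 aggregometry + 4 TEG channels + 1 CAT + 1 urinary thromboxane + 4 soluble + 2 fibrosis = 16.

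**Assumptions.** m = 3, 6 or 12 events (10%, 20% or 40% of 30). Markers are normal, unrelated to outcome, with common pairwise correlation 0, 0.5 or 0.8.

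**Step 1: apparent AUC of the best null marker.** For each marker, AUC = [R − m(m+1)/2] / [m(30−m)], where R is the rank sum in event patients. The direction is chosen from the data, max(AUC, 1−AUC), and the largest of the k values is kept. The denominators are 3×27 = 81, 6×24 = 144 and 12×18 = 216. Results for k = 5, by simulation:

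| Correlation | Median best AUC (3 / 6 / 12 events) | Share of trials with AUC ≥ 0.70 |
|---|---|---|
| 0 | 0.78 / 0.70–0.71 / 0.67 | about 82% / 55% / 28% |
| 0.5 | 0.75 / 0.69 / 0.65 | about 73% / 46% / 23% |
| 0.8 | 0.72 / 0.66 / 0.63 | about 58% / 32% / 17% |

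Under independence the medians are 63/81 = 0.778, 101/144 = 0.701 and 144/216 = 0.667. Repeat runs differ by up to about 0.01 in the median and three percentage points in the shares. The true AUC is 0.50 throughout. With k = 16 the medians are 0.85 / 0.77 / 0.72 if independent and 0.83 / 0.74 / 0.70 at correlation 0.5.

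**Step 2: separation in a multivariable model.** Complete separation was tested by linear programming with independent noise covariates. With three covariates it occurs in 51%, 10% and 2% of trials at 1, 2 and 3 events, and in none at 6 or 12. With five covariates it occurs in 17%, 1% and 0% at 3, 6 and 12.

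**Step 3: how many events to expect.** P(fewer than 6 events) = Σ C(30,x) pˣ(1−p)³⁰⁻ˣ for x = 0 to 5. This is 93%, 43%, 8% and under 1% at assumed risks of 10%, 20%, 30% and 40%. Exact 95% intervals are wide: 3/30 gives 2.1% to 26.5%, and 6/30 gives 7.7% to 38.6%.

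**Step 4: timing.** If a marker has no predictive value but shifts by d SD after the event, a post-event sample gives AUC = Φ(d/√2): 0.64 at d = 0.5 and 0.76 at d = 1. Both shifts are assumed. They show the mechanism and do not estimate anything in this study.

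**The case against.** The strongest reply is that this is a pilot. Only secondary objectives are affected, Section 5.3 plans validation in a larger cohort, and Section 11 leaves treatment to the provider under standard of care. That stands as a limit on the consequence. It does not correct the AUCs and cut-points this study will report.

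A second reply is that independence overstates the optimism. Two ADP concentrations of one assay and four channels of one cartridge are likely to be correlated. This is fair, and the correlated rows belong beside the independent one. The optimism shrinks but remains.

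Four stronger readings are tempting, and the documents do not support them:

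- *The plan uses samples taken after the event.* Section 5.2 permits this by silence; it does not prescribe it.
- *Event-only 12-month assays will make prediction look falsely good.* For the thromboembolic endpoint those assays have no event-free comparators, so a model or AUC could not be estimated at all. TEG and aggregometry are scheduled for everyone at 12 months and are unaffected.
- *Section 6 and Table 1 contradict each other.* The Section 6 sentence is unrestricted and the footnote is not, but Sections 6 and 6.1.3 both defer to Table 1. This needs clarification only.
- *The models will fail through separation.* That is mainly a risk at three or fewer events or with five or more covariates.

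The ROC outcome, the assay readout behind the fibrinolysis rate, and the mapping from BARC types (set out in Section 10.5) to major or CRNM bleeding are mainly missing detail.

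**Conclusion.** The concern holds as a should-fix point about Section 5.2. Followed literally, the plan yields apparent AUCs and cut-points that are biased upward, because nothing controls model size or marker selection. It also leaves the predictor time open. For five null markers, the median apparent AUC lies between 0.72 and 0.78 at 3 events, 0.66 and 0.71 at 6, and 0.63 and 0.67 at 12, over correlations of 0.8 down to 0. These figures rest on assumed event counts and correlations. The direction of the bias does not; its size falls with more events, fewer markers and higher correlation. The point does not show that the study is too small for its serial-change aims, or that any patient's care in it depends on a cut-point.

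**What to change.** In Section 5.2:

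1. Use Firth or exact logistic regression, primarily one marker at a time, with 95% CIs. Penalise any multivariable model and keep it to a very small prespecified covariate set.
2. For the two prediction objectives, use samples taken before the event, with baseline as the main predictor time, and count only later events. Label same-visit marker versus TEE comparisons as cross-sectional association. The platelet-reactivity objective asks only for correlation and can be labelled as such.
3. Name the outcome and marker list for each ROC analysis. Report AUCs with 95% CIs and an optimism correction or permutation test that repeats the marker selection. Label cut-points exploratory.
4. If events are too few to model, report counts with exact CIs and list the event patients' values descriptively. The threshold is for the study statistician; about 6 is one reasonable choice. At 3 events, a bootstrap correction over five null markers still left a mean AUC of 0.65, against 0.57 at 6.
5. Do not use the assays restricted by footnote 3 for thromboembolic prediction. Word Section 6 and Table 1 consistently, and state in Section 4.2.3 which BARC types count.

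The cost is wording, mainly in 5.2 with small edits in 4.2.3 and Section 6, plus modestly different code. No patients, visits or samples are added, provided Table 1 remains the governing schedule; adopting the unrestricted Section 6 sentence instead would add 12-month assays in event-free patients. The downside is that discrimination will look less favourable and, at low event counts, the prediction objectives will be descriptive only. Even at 6 events, a permutation test over five independent markers had only 43% power for one marker with true AUC 0.80.
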